3.5.3 Additional safety assessments

3.5.3.1 *Laboratory variables and vital signs*

The following laboratory variables and vital variables will be analyzed. They will be converted into standard international units.

- Hematology:
 - Red blood cells and platelets and coagulation: hemoglobin, hematocrit, red blood cell count, platelet count
 - White blood cells: white blood cell count, neutrophils, lymphocytes, monocytes, eosinophils, basophils
- Clinical chemistry:
 - Metabolism: glucose, total cholesterol, total protein, albumin, creatine phosphokinase
 - Electrolytes: sodium, potassium, chloride, bicarbonate
 - Renal function: creatinine, blood urea nitrogen, uric acid.
 - Liver function: alanine aminotransferase (ALT) / Serum glutamic-pyruvic transaminase (SGPT), aspartate aminotransferase (AST) / Serum glutamic-oxaloacetic transaminase (SGOT), alkaline phosphatase, lactate dehydrogenase, total and direct bilirubin
- Urinalysis:
 - Urinalysis for quantitative analysis: pH, specific gravity, proteins, glucose, blood and ketones by dipstick
- Vital signs: Temperature, pulse rate, respiratory rate, systolic and diastolic blood pressure, weight

Data below the lower limit of quantitation/detection limit (LLOQ) will be replaced by half of the LLOQ, data above the upper limit of quantification (ULOQ) will be replaced by ULOQ value.

Quantitative analyses

When relevant, for laboratory variables and vital signs variables, descriptive statistics for results and changes from baseline will be provided for each planned visit window, the last value and the worst value (minimum and/or maximum value depending on the parameter) during the on-treatment period.

Analyses according to Potentially clinically significant abnormality (PCSA)

Potentially clinically significant abnormality (PCSA) analyses will be performed based on the PCSA list currently in effect at Sanofi at the time of the database lock. For parameters for which no PCSA criteria are defined, similar analyses will be done using the normal range, if applicable.

Analyses according to PCSA will be performed based on the worst value during the treatment-emergent period, using all measurements (either local or central, either scheduled, nonscheduled, or repeated).

For laboratory variables and vital signs variables, the incidence of participants with at least 1 PCSA during the treatment-emergent period will be summarized regardless of the baseline level and according to the following baseline status categories:

- Normal/missing
- Abnormal according to PCSA criterion or criteria

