1.3 SCHEDULE OF ACTIVITIES (SOA)

| Procedure | Screening (14 to 28 days before Day 1) | Intervention Period (24 Weeks) | | | | | Follow-up (12 weeks) |
|---|--|--------------------------------|------|------|-------|---------|----------------------|
| | | Wk 0 (Day 1) | Wk 1 | Wk 2 | Wk 12 | Wk 24 | |
| Visit ^a | 1 | 2 | 3A | 3B | 4 | 5 (EOT) | 6 (EOS) |
| Screening | | | | | | | |
| Informed consent/assent ^b | X | | | | | | |
| Inclusion and exclusion criteria ^c | X | X | | | | | |
| Demographics | X | | | | | | |
| Medical history ^d | X | | | | | | |
| Prior and concomitant medications | X | X | X | X | X | X | X |
| Dispense e-diary/Participant and/or parents/caregiver e-diary training ^e | X | | | | | | |
| Study intervention | | | | | | | |
| IMP administration/ injection administration and observation training | | X ^{f, g} | | | | | |
| IRT attribution treatment | | X | | | X | | |
| Safety^h | | | | | | | |
| Full physical examination ⁱ | X | X | | | X | X | X |
| Vital signs ^j | X | X | | | X | X | X |
| 12-lead ECG ^k | X | | | | | X | X |
| AE reporting, including SAEs | <=====X=====> | | | | | | |
| Laboratory testing | | | | | | | |
| Hepatitis (HBsAg, HBsAb, HBcAb, HCVAb) and HIV Serology ^l | X | | | | | | |
| Pregnancy test: menstruating participants only ^m | Ser | Ur | | | Ur | Ur | Ur |
| Menstruation status | X | X | | | X | X | X |

| Procedure | Screening (14 to 28 days before Day 1) | Intervention Period (24 Weeks) | | | | | Follow-up (12 weeks) |
|--|--|--------------------------------|----------------|----------------|-------|---------|----------------------|
| | | Wk 0 (Day 1) | Wk 1 | Wk 2 | Wk 12 | Wk 24 | |
| Visit ^a | 1 | 2 | 3A | 3B | 4 | 5 (EOT) | 6 (EOS) |
| Hematology (including basophil/eosinophil counts), biochemistry, urine analysis ^{n,o} | X | | | | | X | |
| Participant's report outcome (PRO) | | | | | | | |
| Severity symptoms score questionnaires (PRO): modified UAS7, ISS7, and HSS7 | X ^p Modified UAS7 (includes ISS7 and HSS7 as components), once daily from Visit 1 to Visit 6 | | | | | | |
| QoL questionnaires ^q : C-DLQI and IDQOL | | X | | | | X | |
| Pharmacokinetics and ADA^r | | | | | | | |
| Serum PK samples for dupilumab concentration | | X | X ^s | X ^t | X | X | X |
| Anti-dupilumab antibody | | X | | | X | X | X |
| Biomarkers | | | | | | | |
| Serum Total IgE ^u | | | X | | | X | |

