Abbreviations: ADA = anti-drug antibodies; AEs = adverse events; AESI= adverse event of special interest; C-DLQI = Children's dermatology Life Quality Index; CRP = C-reactive protein; CSU = chronic spontaneous urticaria; ECG = electrocardiogram; eCRF = electronic case report form; E/D = early discontinuation; EOS = End of Study; EOT= End of Treatment; HBcAb = hepatitis B core antibody; HBsAb = hepatitis B surface antibody; HBsAg = hepatitis B surface antigen; HCVAb = hepatitis C virus antibody; HIV = Human Immunodeficiency Virus; HSS7 = hive severity score over 7 days; IDQOL = Infant's dermatitis quality of life index; IgG anti-TPO = immunoglobulin G anti-thyroperoxydase; Ig E = immunoglobulin E; IMP = investigational medicinal product; ISS7 = itch severity score over 7 days; PK = pharmacokinetic; Q2W = every 2 weeks; Q4W = every 4 weeks; PRO = patient report outcome; ; rtPCR = reverse transcription–polymerase chain reaction; SAE = serious adverse event; Ser = serum; TB = tuberculosis; UAS7 = urticaria activity score over 7 days; Ur = urine.

- a Allowed time window of ± 3 days for each visit of treatment period and ± 5 days for the Follow-up visit.
- b Prior to any screening assessments: all participants ≥ 6 years of age (or above an age determined by the Institutional Review Board [IRB]/Independent Ethics Committee [IEC]) and their parent(s)/caregiver(s)/legal guardian(s) will receive information about the study, on study objective(s) and procedures, to the fullest extent possible, in their language and in terms they are able to understand, and must sign and date the IRB/IEC approved Informed Assent Form (IAF) and Informed Consent Form (ICF), respectively.
- c The clinical status of the participant should be rechecked before first dose of study intervention.
- d Medical history, allergic comorbidities history.
- e Training of participants and parents/caregiver regarding completion of diary to record (a) administration of each dose of drug outside the clinic by parent/caregiver for participants; (b) completion of the assessment of participant reported questionnaires for participants aged ≥ 2 years to <12 years.

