- f* 200 mg Q2W regimen of dupilumab after an initial loading dose of 400 mg on Day 1 for participants weighing ≥ 30 kg and < 60 kg, 300 mg Q4W for participants aged ≥ 2 years to < 6 years weighing ≥ 15 kg and < 30 kg with no loading dose, 300 mg Q4W after an initial loading dose of 600 mg on Day 1 for participants aged ≥ 6 years to < 12 years weighing ≥ 15 kg and < 30 kg, and 200 mg Q4W with no loading dose for participants weighing ≥ 5 kg and < 15 kg at Day 1. The planned last dose will be at Week 22 for Q2W injections and Week 20 for QW4 injections.
- g* Regardless of the participant's age, IMP administration may be performed either at study clinic visits, or by a visiting home nurse or by participant (if ≥ 12 years of age)/participants' parent(s)/caregiver(s)/legally authorized representative trained by the Investigator or designee on how to prepare and administer IMP and how to observe the participant after injection. The injection and observation training will be applicable to the participant (if ≥ 12 years of age)/parent(s)/caregiver(s)/legally authorized representative of participants who wish to administer IMP at home. This training will be performed at Day 1 and may also take place later at any visit in the study if participant (if ≥ 12 years of age)/parent(s)/caregiver(s)/legally authorized representative wish to change to do home injection after initially not choosing this. This training must be documented in the participant's study file. In the cases where the participant (if ≥ 12 years of age)/participants' parent(s)/caregiver(s) prefer not to do home injections, home nurse visits may be arranged to administer the IMP according to the planned dose schedule.
- h* Assessments/procedures should be conducted in the following order: patient-reported outcomes, Investigator assessments, safety, and laboratory assessments (including sample collection for ADA, PK, biomarkers), and administration of study drug.
- i* Physical examinations will include skin, nasal cavities, eyes, ears, respiratory, cardiovascular, gastrointestinal, neurological, lymphatic, and musculoskeletal systems.

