3 STATISTICAL ANALYSES

3.1 GENERAL CONSIDERATIONS

In general, continuous data will be summarized using the number of observations available, mean, standard deviation (SD), median, Q1, Q3, minimum, and maximum. Categorical and ordinal data will be summarized using the count and percentage of participants.

The baseline value is defined as the last available value before the first dose of IMP administration except for efficacy analysis, for which the baseline is defined in [Section 3.3.1.1](#) and [Section 3.3.1.2](#). For participants enrolled but not treated, the baseline value is defined as the last available value before enrollment.

Observation period

The observation period will be divided into 4 segments:

- The **pre-treatment** period is defined as the period up to first IMP administration.
- The **treatment-emergent (TE) period** is defined as the period from the first IMP administration to the last IMP administration +98 days (+112 days for children <30 kg). The treatment-emergent period includes the following 2 periods:
 - The **on-treatment period** is defined as the period from the first IMP administration to the last administration of the IMP +14 days (+28 days for children <30 kg),
 - The **residual treatment period** is defined as the period from the end of the on-treatment period to the end of the treatment-emergent period.
- The **post-treatment period** is defined as the period from the end of the treatment-emergent period.

Unless otherwise specified, analyses will be performed overall and by intervention group:

- 200 mg Q4W
- 300 mg Q4W
- 300 mg Q4W, 600 mg LD
- 200 mg Q2W, 400 mg LD

With the footnote: LD = Loading Dose; Q2W = Every 2 weeks; Q4W = Every 4 weeks.

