3.3.1.2 Itch and Hive Severity Scores and Modified Urticaria Activity Score

For each daily assessment:

- Itch Severity Score items will be converted into numeric values as follows: 0=None; 1=Mild (present but not annoying or troublesome); 2=Moderate (troublesome but does not interfere with normal daily activity or sleep); 3=Intense (interferes with normal daily activity or sleep).

- Hive Severity Scores item will be converted into numeric values as follows:

Table 5 - Numeric values for Hives Severity Scores

Hives severity (number of hives)	Hives severity score
None	0
1-9	1
10-30	2
>30	3

The ISS7 and HSS7 baseline values are the sum of the 7 daily measurements obtained within the 7 days prior to first IMP administration. For subsequent visits, the sum of the 7 measurements on and prior to the target visit will be used (e.g., sum of days 163 through 169 for the visit at Week 24). Day ranges to be used for ISS7 and HSS7 derivations from Week 1 to Week 36 are described in [Section 5.6](#). ISS7 and HSS7 total scores and change from baseline will be summarized quantitatively by timepoint [from baseline to End of Study (EOS)].

Handling of missing daily score: if a participant has more than 50% of non-missing daily scores within 7 days prior to the visit for baseline; and on and prior for subsequent visits, (i.e. 4 or more non-missing scores) then the weekly score will be calculated as the sum of the available scores divided by the number of non-missing daily scores and multiplied by 7. Otherwise, the weekly score will be set to missing.

Additionally, mUAS7 will be computed by summing ISS7 and HSS7 scores. mUAS7 total score and change from baseline will be summarized quantitatively by timepoint.

If one of the ISS7 or HSS7 is missing, the mUAS7 will be set to missing.

mUAS7 total score will also be summarized in category as follows by timepoint:

- 0 = Itch and hive
- 1-6 = Well-controlled urticaria
- 7-15 = Mild urticaria
- 16-27 = Moderate activity urticaria
- 28-42 = Severe activity urticaria

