5.4 APPENDIX 4 DATA HANDLING CONVENTIONS

Analysis windows for time points

Unless stated otherwise, the following analysis windows ([Table 10](#), [Table 11](#), and [Table 12](#)) will decide how the post-baseline scheduled and/or unscheduled visits will be used in the by-visit analyses of efficacy, safety, biomarker and ADA variables.

A measurement (scheduled or unscheduled) will be used if it is available and measurement date is within the analysis window.

After applying these time windows, if multiple assessments are associated with the same time point, the closest from the targeted study day will be used. If the difference is a tie, the value after the targeted study day will be used. If multiple valid values exist within a same day, then the first value of the day will be selected.

If there is no measurement for a given parameter in an analysis window, data will be considered missing for the corresponding visit.

Table 10 - Analyses window definition for participants assigned to PK - Schedule A

Scheduled visit post baseline	Targeted study day	Analysis window in study days
Week 1 (Visit 3A)	8	2 to 46
Week 12 (Visit 4)	85	47 to 127
Week 24 (Visit 5 – EOT)	169	128 to 211
Week 36 (Visit 6 – EOS)	253	≥212

Study days are calculated considering Day 1 as the day of first administration of intervention.

Table 11 - Analyses window definition for participants assigned to PK - Schedule B

Scheduled visit post baseline	Targeted study day	Analysis window in study days
Week 2 (Visit 3B)	15	2 to 50
Week 12 (Visit 4)	85	51 to 127
Week 24 (Visit 5 – EOT)	169	128 to 211
Week 36 (Visit 6 – EOS)	253	≥212

Study days are calculated considering Day 1 as the day of first administration of intervention.

Table 12 - Analyses window definition for participants following the Schedule of Activities from initial version of the protocol dated of 30-Mar-2022

Scheduled visit post baseline	Targeted study day	Analysis window in study days
Week 1 (Visit 3)	8	2 to 11
Week 2 (Visit 4)	15	12 to 22
Week 4 (Visit 5)	29	23 to day 57
Week 12 (Visit 6)	85	58 to day 127
Week 24 (Visit 7 – EOT)	169	128 to 211
Week 36 (Visit 8 – EOS)	253	≥212

Study days are calculated considering Day 1 as the day of first administration of intervention.

Unscheduled visits

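### With dosing on schedule, the on-treatment period ends on the Week 24 target day itself, so 3 of the 7 permitted Week 24 visit days fall outside the last and worst laboratory and vital-sign summaries

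*SAP*

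**What the plan says.** SAP 3.5.3.1 plans descriptive statistics for each planned visit window, and also for "the last value and the worst value (minimum and/or maximum value depending on the parameter) during the on-treatment period". SAP 3.1 ends the on-treatment period at "the last administration of the IMP +14 days (+28 days for children <30 kg"). Protocol 9.2.1 and 9.2.6.1 carry the same definition and the same use of it.

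The timing comes from three other places:

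- **Last dose.** Protocol 1.3, footnote f: "The planned last dose will be at Week 22 for Q2W injections and Week 20 for QW4 injections".
- **Visit window.** Protocol 1.3, footnote a: "Allowed time window of ± 3 days for each visit of treatment period".
- **Day numbering.** SAP 5.4: "Study days are calculated considering Day 1 as the day of first administration of intervention". The Week 24 target is Day 169 in SAP Tables 10 to 13, and SAP 3.3.1.2 uses the "sum of days 163 through 169 for the visit at Week 24".

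In the amended schedule of activities, the row "Hematology (including basophil/eosinophil counts), biochemistry, urine analysis" is marked only at screening and Week 24. Vital signs are marked at screening, Day 1 and Weeks 12, 24 and 36.

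**The concern.** An on-treatment cut-off of one dosing interval after the last dose is a natural choice. Here it lands exactly on the target day of the end-of-treatment visit and leaves no allowance for the visit window. A child who attends within protocol but one to three days late is then treated as off treatment for these summaries, although exposure barely differs from that of a child seen on Day 169.

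This matters more than usual because the amended schedule has a single post-baseline safety draw. If that draw misses the cut-off, no earlier scheduled sample can replace it. For vital signs there is a replacement, but it is the Week 12 value, about 12 weeks older. The last and worst rows would therefore rest on fewer children than neighbouring safety tables (or, for vital signs, on older values), for a reason that has nothing to do with safety or exposure. The study is small (15 enrolled, SAP section 4), and safety is its stated secondary objective.

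**Working it through.** **Inputs.** Last planned dose at Week 22 (Q2W) or Week 20 (Q4W), and visits within ±3 days (Protocol 1.3). Dosing interval tolerance of ±3 days (Protocol 6.1, Table 4). On-treatment extension of 14 days, or 28 days under 30 kg (SAP 3.1). By-visit windows (SAP 5.4). Treatment-emergent extension of 98 days, or 112 days under 30 kg (SAP 3.1).

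**Step 1: reproduce the plan's own figure.** Day = 7 × week + 1. Week 24: 7 × 24 + 1 = 169, which matches the SAP target day.

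**Step 2: end of the on-treatment period with dosing on schedule.**

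| Regimen | Last dose day | Extension | End |
|---|---|---|---|
| Q2W (30 kg and over) | 7 × 22 + 1 = 155 | 14 | 169 |
| Q4W (under 30 kg) | 7 × 20 + 1 = 141 | 28 | 169 |

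**Step 3: permitted visit days lost.** The Week 24 visit may fall on Days 166 to 172, which is 7 days. Days 170, 171 and 172 are after Day 169: 3/7 = 42.9% of permitted days.

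**Step 4: from days to samples.** The documents give no distribution of actual visit days, so any share of samples is an assumption.

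| Assumption | Share after the cut-off |
|---|---|
| All visits on or before Day 169 | 0% |
| Discretised normal on Days 166–172, SD 1 day | 30% |
| Same, SD 2 days | 39% |
| Uniform over 7 days, dose on schedule | 42.9% |
| Dose and visit each uniform ±3 days, independent | (49 − 7)/2 = 21 of 49 = 42.9% |
| Uniform visits, last dose 3 days early | 6/7 = 85.7% |
| Uniform visits, last dose 3 days late | 0% |
| All visits late | 100% |

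**Step 5: which other tables keep a Day 170 to 172 value.**

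- Week 24 by-visit table: the window is Days 128 to 211, so the value is kept.
- PCSA: it uses the treatment-emergent period, which ends on Day 155 + 98 = 141 + 112 = 253, so the value is kept.

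**Step 6: test of a longer window.** Take dose and visit offsets of −3 to +3 days, 49 combinations in all. A sample is lost when visit offset minus dose offset exceeds the added days.

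- Adding 3 days loses differences of 4, 5 and 6: 3 + 2 + 1 = 6 of 49 (12.2%).
- Adding 7 days (last IMP + 21 or + 35) loses 0 of 49, because the largest difference is 6. With the last dose 3 days early, the window ends on 152 + 21 = 138 + 35 = Day 173, past Day 172.

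**The case against.** The best defence is that no safety sample leaves the report. The sentence that restricts last and worst values to the on-treatment period also provides by-visit statistics, and the Week 24 analysis window runs to Day 211. For a child with one post-baseline draw and no unscheduled samples, the Week 24, last and worst laboratory values are the same number, so the by-visit table already shows it. PCSA keeps it too, and all safety analyses are descriptive. This stands, and it confines the problem to the last and worst summaries.

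A reader might infer that 43% of Week 24 laboratory samples drop out, or that about 6 of the 15 children (15 × 3/7 = 6.4) would have no on-treatment laboratory value. The documents support neither. The 43% is a share of permitted visit days. It becomes a share of samples only under an assumed visit pattern, and if late doses and late visits go together in the same child the loss changes, because the cut-off moves with the actual last dose.

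The count of 6 further assumes that all 15 children followed the amended schedule, reached Week 24 and had no unscheduled samples. The first child enrolled on 08-Sep-2022, before the amended protocol of 31-May-2023, and SAP Table 12 provides for participants on the initial schedule. The amendment reduced blood and urine tests, so those children may have earlier on-treatment samples; neither their number nor their laboratory schedule is shown. SAP 5.4 also lets unscheduled samples supply the last on-treatment value.

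The defence does not explain why a protocol-compliant visit should count as on treatment on Day 169 and not on Day 170.

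**Conclusion.** The point holds in a limited form. The coincidence of the cut-off with the Week 24 target day is exact for both dosing frequencies when dosing is on schedule, and it places 3 of the 7 permitted visit days outside the on-treatment period. For a child on the amended schedule with no unscheduled samples, a visit on Days 170 to 172 leaves the last and worst laboratory summaries without a value and moves the last on-treatment vital sign back to Week 12.

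The size of the loss is unknown. Plausible symmetric visit patterns give roughly 30% to 43% of Week 24 samples with dosing on schedule; the logical range is 0% to 100%. No inferential result is affected. This is a cheap correction worth making before database lock, and it does not undermine the safety evaluation.

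**What to change.** In SAP 3.5.3.1, for the last and worst laboratory and vital-sign summaries only, extend the window to last IMP + 21 days (+ 35 days for children under 30 kg). This covers every Week 24 visit within ±3 days even when the last dose was 3 days early. Because Protocol 9.2.1 and 9.2.6.1 contain the present rule, record the departure in SAP 3.8.

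The cost is one sentence in 3.5.3.1 and one row in 3.8. The downside is that values up to one week past the dosing interval count as on-treatment.

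Two simpler-looking alternatives are worse. The full treatment-emergent period runs to Day 253, the Week 36 target (7 × 36 + 1), so a Week 36 vital sign could become the last value. Ending the period at the Week 24 assessment could count off-drug values in children who stop early, since Protocol 7.1.1 encourages them to attend the remaining visits. No ECG wording is needed, because SAP 3.5.3.1 plans no ECG summaries.

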3.6 OTHER ANALYSES

3.6.1 Other variables and/or parameters

3.6.1.1 Immunogenicity analyses

ADA incidence (up to the end of study) and on-treatment ADA incidence (measurements during the treatment epoch) will be provided for the following ADA response categories:

Pre-existing immunoreactivity is defined as:

An ADA positive response in the assay at baseline with all post first dose ADA results negative, OR an ADA positive response at baseline with all post first dose ADA responses less than 4-fold over baseline titer levels.

Treatment-emergent ADA responses are defined as:

A positive response in the ADA assay post first dose, when baseline results are negative or missing.

Treatment-emergent ADA responses are further classified as Persistent, Indeterminate or Transient

- a) Persistent Response- defined as a treatment-emergent ADA response with two or more consecutive ADA positive sampling time points, separated by greater than ($>$) 12-week period (84 days), with no ADA negative samples in between.
- b) Indeterminate Response- defined as a treatment-emergent response with only the last collected sample positive in the ADA assay
- c) Transient Response - defined as a treatment-emergent response that is not considered persistent OR indeterminate

Treatment-boosted response is defined as:

An ADA positive response in the assay post first dose that is greater-than or equal to 4-fold over baseline titer levels, when baseline results are positive.

Titer values (Titer value category)

- Low (Titer <1000)
- Moderate ($1,000 \leq \text{Titer} \leq 10,000$)
- High (Titer $>10,000$)

The following summary will be provided based on ADA population:

- Number (%) of participants with pre-existing immunoreactivity
- Number (%) of participants with treatment-emergent ADA
- The summary statistics (including number, median, Q1, Q3, minimum and maximum) of the peak post-baseline titer for participants with treatment-emergent ADA, and participants with persistent, indeterminate and transient ADA response
- Number (%) of participant with transient treatment-emergent ADA
- Number (%) of participants with persistent treatment-emergent ADA
- Number (%) of participants with indeterminate treatment-emergent ADA
- Number (%) of participants with treatment-boosted ADA
- The summary statistics (including number, median, Q1, Q3, minimum and maximum) of the peak post-baseline titer for participants with treatment-boosted ADA
- The summary statistics (including number, mean, SD, median, Q1, Q3, minimum and maximum) of the ratio of peak post-baseline titer to baseline titer for participants with treatment-boosted ADA
- Listing of ADA peak titer levels and neutralizing antibody status
- Number (%) of participants with neutralizing antibody status

Kinetics of treatment-emergent ADA response

Number (%) of participants with treatment-emergent ADA positive response at each visit will be summarized by each intervention group.

Plot of percentage of participants with treatment-emergent ADA positive response at each visit will be provided by each intervention group.

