- n* Hematology will include hemoglobin, hematocrit, platelet count, total white blood cell count, differential count, and total red blood cell count. Serum chemistry will include creatinine, blood urea nitrogen, glucose, lactate dehydrogenase, uric acid, total cholesterol, total protein, albumin, total and direct bilirubin, alanine aminotransferase, aspartate aminotransferase, alkaline phosphatase, electrolytes (sodium, potassium, chloride), bicarbonate, and creatine phosphokinase. Urinalysis will include specific gravity, pH, glucose, ketones, blood, and protein. In case the urine dipstick test result is abnormal, a urine sample should be sent into the central laboratory for microscopic examination.
- o* Blood volume required is in accordance with "Blood sample volumes in child health research" (1). See [Section 8](#) for additional details.
- p* Assessments of severity symptoms (patient report outcome, PRO) includes completion of modified UAS7 questionnaires over 7 consecutive days for CSU participants. The PRO is to be recorded in the e-diary on the same time of the day. Completion of modified UAS7 should be done by the child or parent(s)/caregiver(s)/legal guardian(s) for participants aged 4 years or older; and by parent(s)/caregiver(s) for participants aged less than 4 years.
- q* Quality of life will be assessed through C-DLQI questionnaires in participants ≥ 4 years to < 12 years of age and IDQOL in participants < 4 years of age.
- r* In the event of any SAE, any AE of severe injection site reaction lasting longer than 24 hours, or any AESI of anaphylactic reaction or systemic allergic reaction that is related to IMP and require treatment, PK and ADA samples will be collected at or near the onset of the event for any additional analysis if required or for archival purposes.
- s* For participants assigned to PK Schedule A (determined by IRT system at Visit 2): Weeks 0, 1, 12, 24, 36.
- t* For participants assigned to PK Schedule B (determined by IRT system at Visit 2): Weeks 0, 2, 12, 24, 36.
- u* Biomarker sample collection is mandatory for participants with body weight ≥ 30 kg and optional for participants with body weight ≥ 15 kg and < 30 kg.

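### SAP 3.6.1.1 requires persistent ADA positives to be more than 84 days apart, but ADA samples are scheduled exactly 84 days apart, so two adjacent on-schedule positives are classed as transient

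*SAP*

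**What the plan says.** SAP 3.6.1.1 splits treatment-emergent ADA responses into three classes.

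- Persistent: "two or more consecutive ADA positive sampling time points, separated by greater than" a "12-week period (84 days), with no ADA negative samples in between".
- Indeterminate: a "treatment-emergent response with only the last collected sample positive in the ADA assay".
- Transient, the residual class: "defined as a treatment-emergent response that is not considered persistent OR indeterminate".

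A response is treatment-emergent only if baseline is negative or missing, so the Week 0 sample cannot supply one of the positives.

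The classes feed listed outputs, among them "Number (%) of participants with persistent treatment-emergent ADA", the matching transient and indeterminate counts, and peak titer by class. SAP 3.6.1.1 gives ADA incidence by response category twice: up to end of study, and on treatment.

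The schedule in Protocol 1.3 has ADA samples at Weeks 0, 12, 24 and 36 and none at Visits 3A or 3B: "Anti-dupilumab antibody | | X | | | X | X | X". Footnote a sets the visit windows: "Allowed time window of ± 3 days for each visit of treatment period and ± 5 days for the Follow-up visit". Footnote r adds event-driven samples: "PK and ADA samples will be collected at or near the onset of the event". SAP Tables 10 and 11 put the three post-baseline ADA visits on Days 85, 169 and 253.

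The SAP does not say whether separation is measured on actual or nominal dates, or whether it runs from the first to the last positive in a run or between neighbouring positives.

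**The concern.** The persistence threshold equals the sampling interval, and the inequality is strict. A child with two positives in a row, sampled on the planned days, therefore cannot meet it. Such a child is not indeterminate either, because the last sample is not the only positive one, so the residual class takes over.

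The labels then run against the evidence. A child positive at Weeks 24 and 36, with no later negative, is transient. A child positive only at Week 36 is indeterminate. A child positive at Weeks 12 and 36 with Week 24 missing is persistent, on less evidence of continuity than two neighbouring positives give.

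At stake are the persistent and transient counts, the peak-titer summaries by class, and any display that uses these classes as ADA variables (SAP 3.6.1.1.1).

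**Working it through.** **Inputs.** Threshold: more than 84 days (SAP 3.6.1.1). Target Days 85, 169, 253 (SAP Tables 10 and 11). Windows: ±3 days at Weeks 12 and 24, ±5 days at Week 36 (Protocol 1.3, footnote a).

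**The plan's own figure.** 12 weeks × 7 = 84 days, as the SAP states.

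**Scheduled gaps.** 169 − 85 = 84 and 253 − 169 = 84. Since 84 > 84 is false, neither neighbouring pair qualifies. Weeks 12 to 36: 253 − 85 = 168, which does.

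**Classes on target days, all three samples available.**

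| Weeks 12, 24, 36 | First-to-last reading | Neighbouring-sample reading |
|---|---|---|
| + + − | transient | transient |
| − + + | transient | transient |
| + + + | persistent (168 days) | transient (84 and 84) |
| − − + | indeterminate | indeterminate |
| + − −, − + −, + − + | transient | transient |

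Two or more adjacent positives end up transient in 2 of 7 non-zero patterns on the first reading and in 3 of 7 on the second.

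**On-treatment analysis.** I take the treatment epoch to hold the Week 12 and Week 24 samples. The only candidate for persistence is + + at a gap of 84 days, which is transient, so on target days persistent cannot occur. The same holds at the primary database lock (SAP 3.7) for any child who has no Week 36 sample yet.

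**If actual dates are used.** Let a and b be the offsets in days of the earlier and later sample; the gap is 84 + b − a.

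- Weeks 12 to 24: range 84 − 6 = 78 to 84 + 6 = 90. Of 7 × 7 = 49 offset pairs, 21 exceed 84, 7 equal it and 21 fall below. Not exceeding 84: 28/49 = 57%.
- Weeks 24 to 36: range 84 − 8 = 76 to 84 + 8 = 92. Of 7 × 11 = 77 pairs, 35 exceed 84, 7 equal it and 35 fall below. Not exceeding 84: 42/77 = 55%.
- Weeks 12 to 36: 168 ± 8 = 160 to 176, always above 84.

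The percentages weight all allowed offsets equally, which is an assumption; the documents give no distribution of visit dates.

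**Would changing > to ≥ be enough?** On nominal days, yes. On actual dates, 21/49 = 43% and 35/77 = 45% of pairs would still fall short.

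**A 76-day threshold, first to last positive.** The shortest in-window gap is 76, so 0 of 49 and 0 of 77 pairs fail. Days 88 and 166 (78 days) and Days 85 and 165 (80 days, the second sample one day out of window) both qualify. Day 85 with an early end-of-treatment sample on Day 130 (45 days) does not.

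**The case against.** The strongest reply concerns importance. The named secondary endpoint is the incidence of ADA over time, and Protocol 9.2.3.2 mentions incidence and treatment-emergent ADA. The three-way split appears only in the SAP, every analysis is descriptive, and the associations with efficacy and safety are optional. Enrollment stopped at 15 (SAP 4), the documents give no ADA rate, and only children with a run of adjacent positives matter. This stands, and it keeps the point minor.

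A second reply is that appointment timing matters only if actual dates are used. That also stands. Protocol 8.4.1.1 has the collection date recorded, so actual dates are plausible, but the SAP does not commit to them. On nominal days no appointment effect arises; every two-positive adjacent run is simply transient.

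A third reply is that three positives in a row still qualify. They do if separation runs from first to last positive, which is unstated, and they cannot arise from the scheduled samples of the on-treatment analysis.

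Two stronger readings are tempting. A reader might infer that the persistent class is empty. The documents do not support that for the end-of-study analysis: a three-positive run spans 168 days, a Week 12 and 36 pair with Week 24 missing also qualifies, and on actual dates some two-positive runs exceed 84 days. A reader might also infer that the immunogenicity results as a whole are compromised. They are not, because whether a child counts as treatment-emergent or treatment-boosted does not depend on the separation rule.

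**Conclusion.** The mismatch follows from the documents' own dates, and nothing elsewhere in them resolves it. On target days, two adjacent positives alone are always transient: 2 of 7 non-zero patterns are affected on the first-to-last reading and 3 of 7 on the neighbouring-sample reading. In the on-treatment analysis, and at the primary lock for children without a Week 36 sample, persistent is unattainable on target days. On actual dates the class turns on a shift of a day or so, with 57% and 55% of in-window pairs not exceeding 84 days under equal weighting.

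Not affected: treatment-emergent and treatment-boosted incidence, by-visit ADA kinetics, the ADA positive/negative split, and the primary PK summary. The number of children affected is unknown and may be zero. Event-driven samples could change individual cases, as could samples from children on the initial protocol schedule, whose ADA times are not given. Severity: minor.

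**What to change.** In SAP 3.6.1.1, replace the separation criterion with one rule for all samples, scheduled or not:

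*Persistent: a treatment-emergent response with two or more consecutive ADA positive samples and no negative sample in between, where the first and last positives in the run are at least 76 days apart by actual collection date (12 weeks less the combined visit-window tolerance of 3 + 5 days).*

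This settles the boundary, the date basis and the meaning of separation together. Every in-window run at Weeks 12 and 24, Weeks 24 and 36, or Weeks 12 and 36 with Week 24 missing then qualifies. A short gap to an early end-of-treatment sample does not. An extra positive can only lengthen the span, so a longer run never gets a lesser class, and no override is needed.

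Leave the indeterminate and transient definitions unchanged. One consequence remains: a short run that ends in a positive early end-of-treatment sample stays transient although no negative follows.

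The cost is one sentence of SAP text and no new data. The class will differ slightly from the strict rule of more than 84 days, so add a footnote if results are compared or pooled with data classified that way.
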